10.2 Subgroup Analyses

The following subgroup analyses will be performed for efficacy endpoints PFS, ORR, and OS:

- Age (≤ 40 , 41 – 64, ≥ 65)
- Race (White vs other)
- Prior line of chemotherapy for advanced disease (0-1 vs ≥ 2)
- Levels of GPNMB expression (25% - $< 50\%$ or $\geq 50\%$)
- Progression-free interval (PFI) after receipt of taxane therapy (≤ 6 months vs > 6 months)
- Prior anthracycline therapy (Yes vs No)
- Estrogen Receptor (ER)/Progesterone Receptor (PR) level (both $< 1\%$ vs either $\geq 1\%$)

- Visceral disease (Yes vs No)
- CNS involvement (Yes vs No)
- Number of disease site (≤ 3 vs > 3)
- ECOG PS (0 vs 1)
- Region (North America vs Other)

The subgroups of PFI, prior anthracycline, and prior line of chemotherapy for advanced disease are determined based on actual clinical data. The subgroup analyses will be performed with the corresponding stratification factors if appropriate. If the number of subjects is too small in a particular stratum to produce reliable estimate, unstratified analysis may be used.

10.3 Progression-free Survival (PFS)

PFS is defined as the time from the date of randomization to documented disease progression, or death due to any cause, whichever is earlier.

10.3.1 Primary PFS Analysis

The primary analysis of PFS will be based on the Independent Review Committee (IRC) assessment according to RECIST 1.1. Unless specified otherwise, all recorded PFS events will be included in the primary analysis regardless of stopping randomized therapy. [Table 3](#) below describes the detailed censoring rules for the primary PFS analysis. The determination of PFS is also detailed in the flow chart in the [Appendix](#) (Section 17).

Table 3: Date of Progression of Censoring for the Primary PFS analysis (IRC)

Situation	Date of Progression or Censoring	Outcome
Disease progression between scheduled disease assessments	Date of progression	Progressed
Death between scheduled disease assessment	Date of death	Progressed
Death before the first planned disease assessment at 6 weeks (plus 1 week window) without any disease assessment	Date of death	Progressed
No baseline disease assessments	Date of randomization	Censored
No post-baseline disease assessments without death before the first planned disease assessment	Date of randomization	Censored
Discontinuation of study treatment without progression (i.e., due to toxicity, withdrew consent, or lost to follow-up) and no further radiographic assessment ^a	Date of last radiological assessment without documented progression disease	Censored
Alternate anticancer treatment started without documentation of disease progression beforehand ^b	Date of last radiological assessment prior to start of further anticancer treatment	Censored
Death or disease progression after missing two or more consecutively scheduled disease assessments ^c	Date of last radiological assessment without documented progression disease prior to death/progression	Censored
Patients who have not progressed and are alive	Date of last radiological assessment without documented progression disease	Censored

a. For a patient who discontinues study treatment without PD and continues to have radiographic assessments, post-treatment radiographic assessments will be considered for PFS analyses according to the rules in this table.

b. Alternate anticancer treatment interventions that are diagnostic (e.g., biopsy) or palliative (e.g., local radiation for painful nodule) will not routinely require censoring unless they are determined to interfere with the assessment of the patients' disease status.

c. Disease assessments are planned every 6 (± 1) weeks for the first 6 months (24 weeks); and every 9 (± 2) weeks, thereafter, until disease progression. The interval of two missed scheduled assessments is calculated according to the scheduled assessment frequency and the corresponding window (1 or 2 weeks depending on assessments scheduled before or after 6 months).

The median PFS by treatment group will be estimated using Kaplan-Meier method and the Kaplan-Meier curves by treatment group will be presented.

The primary inferential comparison of this endpoint will use the stratified log-rank test stratified by the actual stratification factors corrected in the clinical database after randomization. A secondary analysis based on *the stratification factors as randomized* will also be performed ([Section 4.1](#)). Estimation of the hazard ratio for treatment and its corresponding 95% confidence interval will be determined using a stratified Cox proportional hazards model with the same stratification factors.

Subgroup analyses for PFS ([Section 10.2](#)) will be performed and a forest plot will be presented.

10.3.2 PFS Analysis (Investigator)

The analysis approach is the same as the PFS analysis based on IRC assessment.

Additionally, differences between the IRC and investigators assessments of disease progression will be summarized by treatment arm. Such differences will include the early discrepancy rate and late discrepancy rate ([Zhang et al 2013](#)), which are based on the frequency that the investigator's evaluation declares progression earlier or later than the IRC, respectively.

10.3.3 Sensitivity PFS Analysis

Sensitivity analysis will be performed to assess potential sources of bias due to 1) censoring for alternate anti-cancer therapy; 2) symptomatic disease progression.

Alternate anti-cancer therapy prior to documentation of disease progression

It is anticipated some patients may receive subsequent anti-cancer therapy prior to documentation of progressive disease. Censoring alternative anticancer treatment prior to documented progression may be problematic since it ignores the issue of informative censoring and contravenes the basic principle of an intention-to-treat analysis. Patients who stop taking randomized study treatment prior to documented progression frequently do so due to either toxicity of the drug or due to deterioration in the status of their disease. In such cases, the investigator may judge that immediate intervention, commonly in terms of the introduction of a new cancer treatment, is in the best interest of the patient without necessarily waiting for confirmatory radiographic evidence of progressive disease ([Carroll 2007](#)).

To address the above concerns, the following sensitivity analysis will be performed: Death or disease progression that's documented after the initiation of an alternate anti-cancer therapy will be considered as a PFS event.

Symptomatic progression / hospice care events

A sensitivity analysis will be performed with symptomatic deterioration or admission to hospice care considered a PFS event with investigator's disease assessments. Patients with symptomatic deterioration will be considered to have disease progression the day after the date of the last disease assessment showing no evidence of disease progression. For patients who enter hospice care without prior symptomatic deterioration or disease progression per RECIST 1.1, the date of admission to the hospice care will be considered as PFS event date.

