7.2.4.1. Discontinuation of Study Treatment

Reasons for discontinuation of study treatment include:

- Progressive disease, as assessed by the treating investigator in accordance with RECIST 1.1 criteria ([Appendix 3](#));
- Symptomatic deterioration (clinical progression);
 - Note: This category is applicable to patients with a global deterioration of health status requiring discontinuation of treatment. However, per RECIST 1.1 (See [Appendix 3](#)), symptomatic deterioration is not a descriptor of an objective response; it is a reason for stopping study therapy. Thus, every effort should be made to continue disease assessments per protocol until documented objective progression, regardless of any changes in therapy.
- Receipt of alternate anti-cancer treatments;
- Withdrawal request by the patient or the patient's legal representative;
 - Note: Withdrawal of consent for continued treatment should be differentiated from withdrawal of consent for study follow-up, and every effort should be made within the bounds of safety and patient choice to have each patient complete the study follow-up.
- Adverse Event, including the development of dose limiting toxicity (See [Section 8.1.6](#));
- Physician Decision;
- Non-compliance of the patient;
- Pregnancy;
- Death, otherwise not explainable by the above options;
- Patient lost to follow-up. (See below.)

Patients who discontinue CDX-011 should be seen for an End of Treatment Visit. Patients who discontinue study treatment without progression of disease as per RECIST 1.1 should continue Disease Assessment Visits until criteria for disease progression are met. (See [Table 1](#).)

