24. Imaging-based evaluation per RECIST 1.1 should be performed in accordance with the Site Manual provided by Celldex (or designee). Contrast-enhanced CT of the chest, abdomen, and pelvis, as well as all other suspected disease sites is required. MRI exams of the brain, abdomen, and pelvis can be performed in lieu of a CT; however MRI exams of the chest are not recommended. In the event that a chest MRI is performed, a non-contrast chest CT is strongly recommended to evaluate the lung parenchyma. Brain and/or bone scans are required for any patients with a history of metastases to bone and/or brain or where symptomatology raises the suspicion for bone and/or brain metastases. Lesions identified on bone scans should be confirmed by a CT or MRI at baseline, and, if identified as target lesions due to soft tissue component, they should continue to be followed by the same methodology (i.e., CT or MRI scan). However, bone lesions followed as non-target disease may be subsequently followed by bone scans only. Lesions that cannot be imaged but are assessable by clinical exam may be assessed using color photography including a ruler (preferred method) or measured with calipers. Normally, all target and non-target disease sites should be evaluated at each assessment. However, for patients with non-target bone disease, bone scans need only be repeated every twelve weeks. The same method of assessment and the same technique should be used to

characterize each identified and reported lesion at baseline and during follow-up. Target lesions selected for tumor measurements should be those where surgical resection or radiation are not indicated or anticipated.

25. Randomization may be performed up to 5 days prior to initiation of study treatment, but should occur only after confirming all eligibility criteria have been met.
26. Unless otherwise specified, all study assessments should be performed prior to administration of study treatment, and may be performed up to 24 hours prior to treatment administration if assessments remain within the specified visit window.

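### Does the symptomatic-progression sensitivity analysis of PFS fail for want of an event date in patients never rescanned after baseline?

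*SAP*

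**What the plan says.** SAP 10.3 sets the time origin: "PFS is defined as the time from the date of randomization to documented disease progression, or death due to any cause, whichever is earlier".

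SAP 10.3.3 then defines a supportive analysis with "symptomatic deterioration or admission to hospice care considered a PFS event", using the investigator's assessments. A patient who deteriorates symptomatically "will be considered to have disease progression the day after the date of the last disease assessment showing no evidence of disease progression". Hospice admission is dated at admission, but only for patients with neither earlier symptomatic deterioration nor RECIST progression.

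Table 3 in SAP 10.3.1 is headed for the primary IRC analysis; SAP 10.3.2 applies the same approach to the investigator's assessments. Three of its rows matter here:

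- Progression seen between scheduled assessments is an event on the date of progression.
- Death before the first planned assessment (6 weeks plus a 1-week window), with no assessment done, is an event on the date of death.
- The row "No post-baseline disease assessments without death before the first planned disease assessment" is censored at randomization.

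On timing, the screening window in SAP Table 1 runs from Day -28 to Day -1, and footnote 25 adds: "Randomization may be performed up to 5 days prior to initiation of study treatment". Protocol 7.2.4.1 lists symptomatic deterioration as a reason for stopping treatment and says that "every effort should be made to continue disease assessments per protocol until documented objective progression, regardless of any changes in therapy".

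**The concern.** The rule in 10.3.3 looks back to a scan without progression. Someone who deteriorates in the first weeks and is never scanned again has no such follow-up scan. The only earlier scan is the screening one, and counting one day on from it usually lands before randomization. If the screening scan does not qualify, there is no date at all. Falling back on Table 3 would censor the patient at randomization, although 10.3.3 calls the same patient an event.

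The SAP expects some patients of this kind. Section 10.4 describes people who stop for worsening disease without objective progression and whose tumor assessments were never done or not repeated. In an open-label trial, an analysis meant to test bias from symptomatic progression would be weakened if its earliest deteriorations dropped out, particularly if they were more frequent in one arm.

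**Working it through.** **Who is affected.** A first follow-up scan that shows progression gives a date under SAP 10.3 and Table 3; 10.3.3 leaves unstated only which date takes precedence. If Table 3 carries over, death before the first planned assessment without a scan is also dated. What remains is the patient with symptomatic deterioration, no post-baseline scan, no RECIST progression and no death in that first window.

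**The date if the screening scan is the anchor.** Let *s* be the days from scan to first dose (1 to 28) and *r* the days from randomization to first dose (0 to 5), with *s* ≥ *r*. The rule gives an event time from randomization of *r* − *s* + 1 days.

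- Permitted whole-day combinations for *r* = 0 to 5: 28 + 28 + 27 + 26 + 25 + 24 = 158.
- Earliest: *s* = 28, *r* = 0, giving 0 − 28 + 1 = −27 days.
- Latest: *s* = *r*, giving +1 day (5 combinations).
- Zero when *s* = *r* + 1 (6 combinations); negative in the other 158 − 5 − 6 = 147.

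These count schedule combinations, not patients. The reading is also strained: inclusion criterion 2 requires documented progression during or after the last regimen, and the screening scan is the reference for later change.

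**The plan's own figure.** With HR 4.0/6.25 = 0.64 and 2:1 allocation, events = (1.960 + 1.036)² / [(2/3)(1/3)(ln 0.64)²] = 8.98 / (0.2222 × 0.1992) ≈ 203. This agrees with SAP 5 and does not depend on 10.3.3.

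**Effect of the choice of date.** The simulation took 200 and 100 patients, exponential PFS with medians 6.25 and 4.0 months, uniform accrual over 24 months, cutoff at 26 months, 10% dropout at a uniform time, an unstratified Cox model and 2,000 runs per scenario. An assumed number of patients deteriorated at a time uniform on days 7 to 42. Each such event was (a) kept at its recorded date, (b) put at day 1, (c) put at a first scan on days 35 to 49, not before deterioration, or (d) lost. Censoring at randomization gives the same HR as (d).

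| CDX-011 + capecitabine patients | (a) recorded | (b) day 1 | (c) first scan | (d) lost |
|---|---|---|---|---|
| 2 + 1 | 0.641 | 0.641 | 0.640 | 0.637 |
| 6 + 3 | 0.649 | 0.650 | 0.648 | 0.638 |
| 10 + 5 | 0.656 | 0.659 | 0.655 | 0.638 |
| 8 + 2 | 0.671 | 0.675 | 0.669 | 0.644 |
| 12 + 3 | 0.682 | 0.687 | 0.678 | 0.640 |
| 5 + 5 | 0.630 | 0.630 | 0.631 | 0.637 |
| 8 + 7 | 0.633 | 0.633 | 0.634 | 0.638 |

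The first three rows have equal risk in both arms. Rows 8 + 2 and 12 + 3 have twice the risk on CDX-011 (4% vs 2%; 6% vs 3%). Row 5 + 5 has twice the risk on capecitabine (2.5% vs 5%), and 8 + 7 has 1.75 times (4% vs 7%). Monte Carlo error is about 0.002 per HR, and the mean standard error of log HR is 0.141.

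- Recorded date against either alternative: at most 0.687 − 0.682 = 0.005.
- Widest gap between any two kept dates: 0.687 − 0.678 = 0.009, or ln(0.687/0.678) = 0.013 on the log scale, about 0.09 standard errors.
- Kept against lost: up to 0.682 − 0.640 = 0.042.

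**Hand check for 10 + 5.** At day 42 the planning medians leave 200 × 0.858 = 171.6 and 100 × 0.787 = 78.7 patients event-free, so the CDX-011 share of the risk set is 171.6/250.3 = 0.686, against 0.667 at the start. Moving 15 events from day 42 to day 1 changes the expected count by 15 × 0.019 = 0.28. Dividing by 203 × 2/9 = 45.1 gives about 0.006 on log HR. The simulation gives ln(0.659/0.655) = 0.006.

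**The case for a change.** The strongest case for acting is that the text does fail for these patients, and that the failure falls on the earliest deteriorations, the group this analysis was built to include. Table 3 gives unscanned early deaths their own row, yet 10.3.3 has no counterpart for unscanned deterioration. The hospice rule does not help, because it excludes patients with prior deterioration. A programmer could pick an invalid time, delete the patient or censor at randomization. If the event were lost, the HR could move by up to 0.042 in the scenarios tried, and one or two sentences would rule that out.

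Part of this stands: no date is written for the never-rescanned patient. The rest is weaker. The clash with Table 3 is the override that any sensitivity analysis makes. For a patient who has a clean follow-up scan and then stops without progression or further scans, Table 3 also censors and 10.3.3 also replaces the censoring with an event, without difficulty. Event status is therefore settled, and losing the event would go against 10.3.3. A sensible date is close at hand too. Table 3 already treats randomization as the last progression-free point when there is no follow-up scan, so the 10.3.3 rule extends naturally to the day after randomization. The recorded date of deterioration would also serve, if the case report form captures it; that form is not among the documents.

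**Conclusion.** This is a missing detail that analysts would fill sensibly, and no change to the plan is needed. It concerns a small, uncounted group in one supportive analysis outside the multiplicity procedure, and the protocol's instruction to keep scanning works to keep that group small. The event status is fixed by the text. Among the plausible dates, the HR differs from its value at the recorded date by at most 0.005, and by at most 0.009 between the two extremes, against a standard error of log HR of about 0.14.

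The sizes rest on assumed counts of 3 to 15 patients in 300, on deterioration between days 7 and 42, and on an unstratified model, whereas the SAP stratifies. The table shells are a separate document and could not be checked for a programming rule. The primary IRC analysis of PFS, the tests of ORR and OS, and the 203-event target do not depend on this point.

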10.4 Objective Response Rate (ORR)

ORR will be estimated based on the proportion of patients in each treatment arm with measurable disease at baseline whose best overall response during the course of study treatment is complete response (CR) or partial response (PR). Tumor response will be assessed using RECIST 1.1. The primary analysis of ORR will be based upon evaluations by the IRC regardless of tumor response (CR or PR) confirmation. The secondary analysis of ORR will be based on the confirmed (no sooner than 28 days later) tumor response (CR or PR). Supplemental analysis will be performed based on investigator's review.

Exact 95% confidence intervals of ORR will be calculated by treatment arm using Clopper-Pearson method. The inferential comparison of the observed ORRs will be made using the Cochran-Mantel-Haenszel Chi-square test, stratified by the randomization stratification factors.

Subgroup analyses will be performed for the list of subgroups specified in [Section 10.2](#). Waterfall plots will be used to depict graphically for individual patients their maximum percentage shrinkage from baseline in the sum of the longest diameters in target lesions.

Best overall response will be classified as 'not evaluable / unknown' for patients with early progression or early death. Early progression will include patients who discontinue study treatment due to worsening disease but without objective evidence of disease progression, and their best overall response cannot be determined because tumor assessments were either incomplete or were never performed or not repeated. Similarly, early death will include patients who die without objective evidence of disease

progression beforehand, and their best overall response cannot be determined because tumor assessments were either incomplete or were never performed or not repeated.

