10.1.4. Disease Assessment Visits

Disease assessments will be performed every 6 (± 1) weeks for 6 months and every 9 (± 2) weeks thereafter, until progression. Patients who discontinue study treatment without documented progression of disease as per RECIST 1.1 should continue to have Disease Assessment Visits until such criteria are met, regardless of intervening changes in therapy.

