12.5. Statistical Methods

12.5.1. Efficacy Analysis

Progression-free survival

PFS is defined as the number of months from randomization to the earlier of disease progression or death due to any cause. The primary analysis of PFS will be based on PFS events determined by the IRC according to RECIST 1.1 ([Eisenhauer, Therasse et al. 2009](#)). Patients whom enter hospice care, or other such similar care, without prior objective evidence of disease progression will be considered to have disease progression for purposes of the primary analysis of PFS. Unless specified otherwise, all recorded PFS events will be included in the primary analysis regardless of stopping randomized therapy. Patients who initiate alternate anticancer therapy in the absence of documented progression will be censored at the latest disease assessment prior to initiation of such therapy. Patients who were last known to be alive and progression-free will be censored at the latest disease assessment. Patients with no baseline or post-baseline disease assessments will be censored at the randomization date unless death occurred prior to the first planned assessment (in which case the death will be considered a PFS event). A secondary analysis of PFS will be

performed based on PFS events determined by the local investigator. PFS will be summarized descriptively using the Kaplan-Meier method. The primary inferential comparison between treatment arms will use the log-rank test stratified by the randomization stratification factors. The hazard ratio for treatment will be estimated using a stratified Cox proportional hazards model.

Objective response rate

ORR is defined as the proportion of patients who achieve a best overall response of complete or partial response according to RECIST 1.1. The primary analysis of ORR will be based upon evaluations by the IRC. Inferential comparisons between treatment arms will be made using the Cochran-Mantel Haenszel chi-square test, stratified by the randomization stratification factors.

Duration of objective response

DOR is defined as the number of months from the time criteria are first met for either CR or PR, until the first date that PD is objectively documented. Patients without documented disease progression will be handled as described above for the PFS analysis. The duration of objective response will be summarized descriptively using the Kaplan-Meier method. Inferential testing of DOR is not planned.

Overall survival

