10.5 Duration of Response (DOR)

DOR will be calculated for patients who achieve CR or PR regardless of confirmation. For such patients, DOR is defined as the number of months from the start date of PR or CR (whichever response is recorded first), to the first date that progressive disease (PD) or death is documented.

The same censoring rules of the primary PFS analysis will be applied to DOR.

Median DOR will be estimated according to the Kaplan-Meier method. Inferential comparison between treatment arms for DOR is not planned.

As noted previously, the primary analysis of DOR will be based on the time point and best overall responses and PFS events determined by blinded independent central review. A supplemental analysis of DOR will be performed based on investigator assessments using the same data cutoff and censoring rules specified in PFS for the primary analysis.

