14 CHANGE FROM PROTOCOL OR APPROVED SAP

Version 1.1 has a clarification of ORR analysis regarding measurable disease in Section 10.4.

- Version 1.0: ORR will be estimated based on the proportion of patients in each treatment arm whose best overall response during the course of study treatment is complete response (CR) or partial response (PR).
- Version 1.1: ORR will be estimated based on the proportion of patients in each treatment arm with measurable disease at baseline whose best overall response during the course of study treatment is complete response (CR) or partial response (PR).

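### SAP 10.4 limits best overall response to the course of study treatment, so a first response on a required scan after treatment has ended is a non-response for ORR, which the protocol's definition does not provide for

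*SAP*

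**What the plan says.** - **ORR in the SAP (10.4).** A responder is a patient "whose best overall response during the course of study treatment is complete response (CR) or partial response (PR"). The primary ORR uses IRC reads and does not require confirmation; confirmed ORR is a secondary analysis.
- **ORR in the protocol (12.5.1, and in substance the synopsis).** "ORR is defined as the proportion of patients who achieve a best overall response of complete or partial response according to RECIST 1.1". No treatment window is attached.
- **Scans after stopping (protocol 10.1.4).** "Patients who discontinue study treatment without documented progression of disease as per RECIST 1.1 should continue to have Disease Assessment Visits", and they do so until RECIST progression even if therapy changes. Protocol 7.2.4.1 and Table 1 footnote 4 say the same. Protocol 12.4.1 commits to ascertaining outcomes in all randomized patients even when they stop protocol therapy early.
- **PFS (SAP 10.3.1, Table 3, footnote a).** For patients who stop without progression, "post-treatment radiographic assessments will be considered for PFS analyses according to the rules in this table".
- **DOR (SAP 10.5).** "DOR will be calculated for patients who achieve CR or PR regardless of confirmation", and "The same censoring rules of the primary PFS analysis will be applied to DOR". No on-treatment limit is stated.
- **Declared changes (SAP 14).** "Version 1.1 has a clarification of ORR analysis regarding measurable disease in Section 10.4". The treatment-period wording appears in both SAP versions quoted there and is not listed as a departure from the protocol.
- **Testing (SAP 10.1).** If PFS is positive, ORR and OS are tested by the Hochberg procedure. ORR is then tested at 0.05, or at 0.025 if the OS p-value exceeds 0.05.

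**The concern.** The SAP narrows a formally tested endpoint relative to the protocol, and the narrowing conflicts with how the rest of the plan treats the same scans. They are required, and they count for PFS, but a first response on one of them does not count for ORR.

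The patients affected are not a random subset. SAP 10.3.3 itself says that patients who stop before documented progression often do so because of toxicity or deterioration. A rule that depends on when treatment stopped can therefore act differently in the two arms if their stopping patterns differ.

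There is also an ambiguity. SAP 7.1 defines study treatment as CDX-011 or capecitabine, but no section says when its course ends. In an open-label trial, the classification of a response close to the last dose should not be left to a programming decision.

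**Working it through.** **1. Is there a figure to reproduce?** Not for ORR. The only design calculation is for PFS. With HR = 4.0/6.25 = 0.64, 2:1 allocation, two-sided alpha 0.05 and 85% power, the Schoenfeld formula gives

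(1.960 + 1.036)² / [(2/3)(1/3)(ln 0.64)²] = 8.98 / (0.2222 × 0.1992) ≈ 203 events.

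This matches the plan and does not depend on the ORR definition.

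**2. When could the course of treatment end?** Take a CDX-011 patient with infusions on Days 1 and 22 who stops during cycle 2, counting days from the first dose. The documents suggest three end points:

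| Possible end of course | Source | Day |
|---|---|---|
| Last dose | SAP 7.1, literal reading | 22 |
| End of exposure | SAP 11: 22 − 1 + 21 = 42 days | 42 |
| Latest End of Treatment visit | Table 1 footnote 6: 22 + 28 | 50 |

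**3. A scan clearly after treatment.** The week-12 scan falls nominally on Day 85 (12 × 7 + 1), with a window of ±7 days, so Days 78 to 92. Day 78 is later than Days 22, 42 and 50. For capecitabine, cycle 2 Day 14 is Day 35. Its three end points are Days 35, 42 and 63 (35 + 28), and Day 78 is later than each. With no new therapy and no earlier progression, a first IRC-read PR on this scan is treated as follows:

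- protocol 12.5.1: responder;
- SAP Table 3, footnote a: the scan is used for PFS;
- SAP 10.4: non-responder, whichever end point is chosen.

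**4. A scan near the last dose.** For the same CDX-011 patient the week-6 scan is nominally Day 43, window Days 36 to 50. If the course ends at last dose, the whole window is outside it. Under the exposure formula, Days 36 to 42 are inside and Day 43 is one day outside. If the course ends at the End of Treatment visit, the scan is inside provided that visit is not earlier than the scan. The text does not settle which applies.

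**5. Effect on the ORR test (illustration only).** The documents give no ORR rates, so assume true ORR of 15% on capecitabine (n = 100) and 30% on CDX-011 (n = 200). The unstratified two-proportion power is Φ[(Δ − 1.96·SE₀)/SE₁], with SE₀ pooled and SE₁ unpooled. With no loss, Δ = 0.15, SE₀ = √(0.25 × 0.75 × 0.015) = 0.0530 and SE₁ = √(0.15 × 0.85/100 + 0.30 × 0.70/200) = 0.0482. Power is Φ(0.955) = 0.83.

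| Responses lost to the window | Power at 0.05 | Power at 0.025 |
|---|---|---|
| None | 0.83 | 0.74 |
| 1 point, CDX-011 only (2 of 200) | 0.78 | 0.68 |
| 2 points, CDX-011 only (4 of 200) | 0.72 | 0.61 |
| 3 points, CDX-011 only (6 of 200) | 0.66 | 0.54 |
| 2 points in each arm | 0.86 | 0.77 |
| 2 points, capecitabine only (2 of 100) | 0.92 | 0.87 |

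A few responders are enough to move the test, and the direction depends on which arm loses them.

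**The case against.** The strongest reply is that an undefined phrase should not be read as a strict rule. The exposure formula and the End of Treatment visit both suggest a course that runs past the last dose. Protocol Section 12 lets the SAP modify the plan and requires an amendment only for major changes to the primary endpoint or its analysis. ORR is secondary and is tested only if PFS is positive.

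Much of this stands, and it rules out several stronger readings that a reader might infer:

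- **That a PR on the Day 43 scan is certainly lost, or that the arms are treated unequally because this scan is 21 days after the last infusion (Day 22) but 8 days after the last capecitabine dose (Day 35).** Both hold only if the course ends at last dose. The exposure formula gives 42 days in either arm.
- **That confirmation is blocked.** The sentence on confirmed ORR sets only a minimum 28-day interval. It does not say that the confirming scan must be on treatment.
- **That ORR and DOR rest on different responders.** This is possible, because SAP 10.5 states no window. But 10.5 also refers to best overall responses by central review, so the 10.4 window could carry over. The mismatch is inferred from silence.
- **That ORR is biased against CDX-011 by a known amount.** The documents give neither the rate of early stops nor the rate of first response after stopping, in either arm.

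The objection does not remove the week-12 case, which is excluded under every end point considered. Reading the phrase as the course of the study would remove it, but that is strained given SAP 7.1. The freedom to modify the protocol also does not explain a departure that SAP Section 14 leaves unlisted.

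**Conclusion.** The point holds as a conflict of definitions. As written, SAP 10.4 turns a first IRC response on a required scan, clearly after treatment has ended and before any new therapy, into a non-response. The protocol would count it. For scans near the last dose the classification is open, because the end of the course is not defined.

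The conclusion rests on taking study treatment to mean the two drugs, as SAP 7.1 does. The number of patients affected is unknown and may be small, and the direction of any effect on the arm comparison cannot be determined from the documents. The power figures above rest on assumed rates and show only that the effect could go either way. The primary PFS analysis and the sample size are untouched. The rule should be corrected before the analysis because ORR carries a formal test.

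**What to change.** In SAP 10.4, replace the treatment-period limit with a window such as: the best IRC-read response from randomization to the earliest of IRC progression, start of alternate anticancer therapy or data cutoff, whether or not study treatment has been stopped. Handle alternate therapy as in Table 3, including footnote b. Use the same window for confirmed ORR and for selecting the DOR patients, which also settles the question left open in 10.5.

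Deleting the phrase alone would not be enough. Patients who stop without progression "should continue to have Disease Assessment Visits until such criteria are met, regardless of intervening changes in therapy", so responses to a later therapy could then be credited to the randomized arm.

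The on-treatment version may be kept as a sensitivity analysis. If so, define when the course ends and list the analysis in Section 14.

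The cost is one SAP sentence and one programming window. No new data are needed, because the scans are already required and already used for PFS.
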